11.2 Please describe your matching and sampling strategies

There will be no requirement to create matched groups due to the repeated measures study design. Each participant will act as their own control.

11.3 Please outline how you will account for potential bias, confounding factors and missing information

Bias

- Double-blinded study

-The different α -lactal bumin dosages to be matched for taste. An external researcher is to provide participants with the supplement to ensure the research team remains blinded to the experimental dosage.

- Diet – As protein and carbohydrates can influence the TRP:LNAA ratio, participants will be asked to come in fasting for a period of 3 hrs before the alpha-lactalbumin supplement consumption.

- Light will be controlled for after the supplement consumption and screen usage or viewing will be restricted to limit the impact of light on endogenous melatonin levels

Missing values will not be substituted in any circumstance (missing or otherwise). There are no planned data cleaning processes, with raw values only to be analysed.

11.4 Please include your statistical power calculation

A paired t-test achieves **85%** power to infer that effect size is above the mean difference of 0.5. When the total sample size of a cross-over design is **16**, the actual mean difference is 0.024, the square root of the within **mean square error** is **0.05**, and the significance level further adjusted from **0.05** to **0.01** to account for repeated comparisons within the group.

12. Data Linkage:

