6.1 The methodological approach

A double blind crossover design has been selected. The double-blinded approach means both the researchers and participants will not know which dosage of the supplement is being received. Through a crossover design, each participant will receive all four dosages of the experimental supplement (α -lactalbumin), on four separate occasions, separated by a washout period of no lesser than 3 days (17, 18). As is the nature of a crossover trial, each participant will serve as their own control.

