7.3 The sample size and statistical or power issues

Sixteen participants are to be recruited as per the statistical power analysis outlined in 11.4. This statistical power analysis was completed in consultation with a Deakin IPAN biostatistician and was performed using G-Power Analysis and Sample Size Software (Version 3.1).

7.4 Your participant recruitment strategies and timeframes (as required in addition to that outlined in the HREA)

[name] (student researcher) will be the primary researcher involved with recruitment. Participants will be recruited through flyers (Appendix 5) placed at Deakin University, local gym settings and sporting clubs, with online platforms (e.g., social media) also used to reach a wider audience. With permission from university unit chairs within the School of Exercise and Nutrition Sciences (see attached Organisation Consent Form), recruitment talks will be completed during lectures and classes within relevant units. Recruitment posts will be uploaded on CloudDeakin pages with permission from unit chairs. All interested individuals will be provided with a plain language statement (Appendix 6) and are to return a consent form to either [name] or [name]. No data collection will take place before written consent is received by the research team. Recruitment will commence in February 2024 (on approval of ethics) and will continue until a sample size of 16 individuals are recruited.

Before the first participant is recruited, this study will be registered within the ANZCTR

7.5 Your approach/es to provision of information to participants and/or consent (as required in addition to that outlined in the HREA)

Any interested individuals will be provided with a digital and hard copy of the plain language statement and consent form to keep (via REDCap). The plain language statement outlines the study design, contact details and states that an individual's decision to be involved in the study will not jeopardise their relationship with Deakin university and the research team. The consent form is to be signed and returned before any data collection is commenced.

7.6 If necessary, the type of consent provided to different participant groups, when and where, and any arrangements to confirm that consent

Written consent. All participants will be provided with a plain language statement and are to sign a consent form before participating in the trial.

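### The 85% power in protocol section 11.4 does not follow from its stated inputs, which give about 9% (two-sided); the inputs need defining or correcting

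*Protocol*

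**What the plan says.** Section 11.4 of the protocol is the only sample-size justification. It states that "A paired t-test achieves 85% power to infer" an effect described in these words: "power to infer that effect size is above the mean difference of 0.5". Its inputs are a crossover total ("When the total sample size of a cross-over design is 16"), a difference ("the actual mean difference is 0.024"), a root within mean square error of 0.05, and a significance level lowered from 0.05 to 0.01 for repeated comparisons. It does not state whether the test is one- or two-sided, which two doses are compared, or the scale of the 0.5.

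Section 7.3 relies on it: "Sixteen participants are to be recruited as per the statistical power analysis outlined in 11.4". Section 9.3 treats 16 as the number to be restored if participants withdraw. Section 6.1 gives the design ("each participant will receive all four dosages of the experimental supplement"), so any comparison of two doses has 16 pairs.

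**The concern.** Two things in section 11.4 stand out. The assumed difference, 0.024, is about half of one within-participant standard deviation. An effect of that size with 16 pairs at the 0.01 level cannot plausibly give 85% power. The paragraph also contains two numbers that it calls a mean difference, 0.5 and 0.024, which differ by a factor of about 20.

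Sixteen has no other support in the protocol. If the inputs are right, the study has much less ability to separate two doses differing by 0.024 than an ethics committee or reader would believe. If an input is mistyped or unlabelled, nobody can tell from the document which one, or what difference in the TRP:LNAA ratio the study was sized to detect. That matters for a study whose aim is to find an optimal dose and whose first hypothesis predicts a plateau at about 40 g.

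**Working it through.** **Inputs** (section 11.4 unless noted): n = 16 pairs (design from section 6.1); difference δ = 0.024; root within-MSE σ = 0.05; α = 0.01; claimed power 85%. Sidedness is not stated, so both were computed.

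**Method.** For a paired t-test, the noncentrality is δ / (SD_diff / √n) and power comes from the noncentral t distribution with n − 1 = 15 degrees of freedom. Each participant takes four doses, so a crossover or mixed model would have more error degrees of freedom. Results with 42 are shown as a more generous variant.

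**Step 1: attempt to reproduce 85%.** The difference of two measurements, each with within-participant SD 0.05, has

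- SD_diff = √2 × 0.05 = 0.0707
- standardised effect = 0.024 / 0.0707 = 0.34
- noncentrality = 0.34 × √16 = 1.36
- two-sided 0.01 critical value on 15 df = 2.95

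The noncentrality is well below the critical value. Power is 8.7%, not 85%.

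**Step 2: more generous readings, all with n = 16 and α = 0.01.**

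| Reading | Two-sided, 15 df | Two-sided, 42 df | One-sided, 15 df | One-sided, 42 df |
|---|---|---|---|---|
| 0.024 with SD_diff 0.0707 | 8.7% | 10.2% | 13.8% | 15.6% |
| 0.024 with 0.05 taken as SD_diff | 19.4% | 23.2% | 28.2% | 32.0% |
| 0.5 taken as the standardised effect | 21.4% | 25.6% | 30.7% | 34.8% |

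The largest value is about 35%. A normal approximation, which is optimistic at this sample size, gives at most 37%. Ignoring the stated adjustment and testing at 0.05 does not help enough either. With 15 df, 0.024 gives 24.6% to 43.5% two-sided and 36.4% to 57.4% one-sided, and a standardised 0.5 gives 46.5% and 60.4%.

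**Step 3: the 0.5.** Taken literally, the sentence describes showing a difference above 0.5 when the true difference is 0.024, for which power is essentially zero. As a raw difference tested against zero, 0.5 gives power of essentially 100%. As a standardised effect it has a natural origin, 0.024 / 0.05 = 0.48, which rounds to 0.5; that is the third row of the table. None of these gives 85%.

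**Step 4: what would give 85% with n = 16 and two-sided 0.01 (15 df).**

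- With SD_diff = 0.0707, the difference must be 0.072. Check: 0.072 / 0.0707 × 4 = 4.07, and power is 85.0%. The ratio to the stated difference is 0.072 / 0.024 = 3.
- With 0.05 as SD_diff, the difference must be about 0.051.
- With the difference kept at 0.024, the root within-MSE must be about 0.017 in place of 0.05.

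**The case against.** The strongest reply is that the fault may be a missing label and not a sample size that is too small. Section 4.3 sets doses of 10, 20, 30 and 40 g and hypothesises a linear relation before a plateau. If 0.024 is the difference per 10 g step, then 10 g and 40 g differ by 3 × 0.024 = 0.072, and every other input except the 0.5 gives 85.0%. This may be what was calculated. But section 11.4 calls 0.024 the actual mean difference and mentions no step, so the match is an inference and could be coincidence. It does not make the sentence right as written. It does mean that the authors must say what 0.024 is before a low power figure is written in.

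Four stronger readings are tempting, and the document does not support them:

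- **That two-sided power, at most about 23% with 0.024, is the ceiling.** Section 11.4 does not state sidedness, and one-sided readings go higher.
- **That 0.5 is impossible beside 0.024.** It is also called an effect size, and 0.48 rounds to 0.5. It is mislabelled or ambiguous.
- **That 0.01 is wrong because four doses give six pairs (0.05 / 6 = 0.0083).** The protocol commits to no set of six pairwise tests. Section 9.1 has five blood timepoints per session, and 0.05 / 5 = 0.01. The basis of 0.01 is unstated, which is different from wrong.
- **That the study will miss a true difference nine times in ten.** The 9% belongs to the paired t-test in section 11.4. Section 11.1 plans a mixed model over all four doses, whose power depends on the contrast tested.

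**Conclusion.** The point holds. The 85% in section 11.4 does not follow from the numbers beside it. With 0.024 as the difference between the two doses compared and 0.05 as the root within-MSE, power at 0.01 is about 9% two-sided and 14% one-sided. Taking 0.05 as the SD of the differences, or 0.5 as a standardised effect, brings it to no more than about 35% by exact t. No choice of sidedness or error degrees of freedom closes the gap.

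This rests on the test being the paired t-test that section 11.4 names, with 16 pairs. A reader might infer that the study is necessarily too small. The document does not establish that, because an input may be mistyped or 0.024 may be a per-step figure. What is established is that the only justification for 16 participants is wrong as written and must be corrected.

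**What to change.** Keep 16 participants. Rewrite section 11.4, and align the reference to it in section 7.3, so that it states:

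1. which contrast is powered (which two doses, or a trend across doses);
2. what 0.024 and 0.5 are and on what scale, or delete the 0.5;
3. whether 0.05 is the root within-MSE or the SD of the paired differences;
4. whether the test is one- or two-sided;
5. how many comparisons, and which ones, lie behind 0.01.

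Then take one of two routes:

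- **If 0.024 is the difference between the two doses compared and 0.05 is the root within-MSE**, replace the claim with: *With 16 participants, a root within-MSE of 0.05 and a two-sided significance level of 0.01, a paired comparison has 85% power for a TRP:LNAA difference of 0.072; power for a difference of 0.024 is about 9%.*
- **If an input is wrong, or 0.024 is the difference per 10 g step** (so that 10 g against 40 g is 0.072), correct or label that input and show the calculation.

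The cost is a rewording of two sections and no extra participants. On the first route the stated power becomes much less favourable.

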12.1 What linkages are planned or anticipated?

N/A

13. Outcome measures:

13.1 Please describe your outcome measures

Primary outcome measures include:

-Amino acid analysis (i.e., plasma TRP:LNAA ratio)

Secondary outcome measures include:

-Plasma melatonin

-Palatability, appetite, and preference of the different alpha-lactalbumin supplement dosages

14. For research involving an unapproved therapeutic good (such as a drug, device or biological): 14.1 Does this project involve an unapproved therapeutic good requiring a Clinical Trial Notification (CTN)? (See the Clinical Trials webpage for more information about CTNs)

 \boxtimes Yes – go to the next question.

□ No – skip to Section 15 (results, outcomes and future plans)

14.2 Is Deakin intended to be the Sponsor?

⊠ Yes – go to the next question

□ No – skip to Section 15 (results, outcomes and future plans)

14.3 If Deakin is intended to be the Sponsor and the research requires a Clinical Trial Notification (CTN), has the CTN, Clinical Trial Sponsorship Request Form and Protocol been submitted to [contact] for assessment?

□ Yes – assessment completed and the CTN must now be submitted to the Therapeutic Goods Administration (TGA) by Deakin (as Sponsor). Please attach evidence of assessment and the CTN form. You will be contacted by the Human Research Ethics Office regarding submission of the CTN to the TGA.

If not, please submit the draft CTN, Clinical Trial Sponsorship Request Form and Protocol to [contact] for assessment before submitting this application to DUHREC. See the Clinical Trials webpage for further information. The Clinical Trial Sponsorship Request Form can be requested by contacting [contact].

14.4 What is/are the drug(s) and/or device(s):

- Approved name BiPRO Alpha 9000
- Trade name (if any) N/A
- Manufacturer Agropur
- Supplier of drug/device (e.g. manufacturer/pharmacy) Agropur
- Approved therapeutic indication, dosage/duration in Australia N/A
- Believed mode of action Increased tryptophan availability → increases melatonin synthesis (tryptophan active ingredient)
- Dosage regimen 10g, 20g ,30, 40 g (tryptophan <1.9 g)
- Mode of excretion N/A
- Known adverse events None
- Known contra-indications or warnings Milk protein allergy and lactose intolerance
- If arrangements have been made for a Pharmacy Department to receive or dispense the drugs involved in this project, explain how the drugs will be received and dispensed for the purposes of the research project N/A

15. Results, Outcomes and Future Plans:

15.1 Please outline your plans for return of results of research to participants – include an ethically defensible plan in accordance with National Statement 3.1.65 or 3.2.15 or 3.3.36-3.3.61, as appropriate.

The research staff will not use the results to diagnose any medical conditions.

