4.3 The research questions/aims/objectives/hypothesis

Research Question: What is the optimal dosage and timing of evening alpha-lactalbumin supplementation to increase the serum TRP:LNAA ratio?

Aim: To identify the optimal dosage of evening alpha-lactalbumin supplementation required to increase the serum TRP:LNAA ratio in healthy active population.

Objectives:

a) To study the dose response of 4 different doses i.e. 10, 20, 30, 40 g of ALAC supplementation on the TRP:LNAA ratio.

b) To observe the difference between the serum melatonin levels 3 hrs post consumption of 4 different ALAC dosages.

c) To test the palatability and appetite post 4 different dosages of ALAC supplementation.

Hypothesis:

1. There will be linear relationship between increasing ALAC dosages and serum TRP:LNAA ratio before reaching a plateau at ~40g.

2. Higher doses of ALAC will increase TRP:LNAA ratio for a longer time period

3. The palatability, appetite and preference will reduce at higher ALAC doses

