7.2 The inclusion and exclusion criteria

Inclusions: Participants must be aged 18-35yrs, recreationally active i.e. completing at least 150 to 300 min moderate-intensity activity or 75–150 min of vigorous-intensity activity a week, plus muscle-strengthening activities 2 or more days a week (Tier 1 activity level) (12). *Exclusions:* Partipicants must not be facing any existing sleeping disorders such as insomnia or consuming any nutraceutical or herbal sleeping aids such as melatonin gummies, chamomile or other herbs which could influence exogenus melatonin production (13). Participants will be screened using the Pittsburgh Scale Quality Index (PSQI) questionnaire and a score of >5 will be excluded from the trial (14). Excessive beer or wine consumption (>17 standard drinks per week), dairy allergy, high caffeine use (e.g., >5 mg·kg-1·d-1), antidepressant or sleep medication use, current or recently finished night shift work (14), recent transmeridian travel, fluctuating bedtimes, and pregnancy are also exclusions from this trial due to confounding influences that may have on the circadian rhythm, exogenous melatonin production or the plasma TRP:LNAA ratio (15).

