8.1 The participant commitment

Methods

Briefly, the screening phase will involve determination of study eligibility and will be administered via an online questionnaire. Upon selection post screening, each participant will be contacted to be explained the experimental protocol and to be scheduled to report to Deakin University (Burwood campus) on four separate occasions for the intervention separated by a washout period of no lesser than 3 days (17, 18).

Screening Session

To determine participant eligibility, participants will be screened, upon consent, using online questionnaire (Appendix 1) on REDCap to assess their eligibility for this study. The screening questionnaire will also involve questions around their training status to exclude any participants who are not recreationally active i.e., completing at least 150 to 300 min moderate-intensity activity or 75–150 min of vigorous-intensity activity a week, plus muscle-strengthening activities 2 or more days a week which classifies them as Tier 1 activity level. Sleep quality will be screened through the Pittsburgh Sleep Quality Index (Appendix 2) to exclude any participants with as PSQI score >5 as well as the presence of any pre-existing sleeping disorders such as insomnia will be screened at this stage.

Experimental Measures

Following screening, shortlisted participants with confirmed eligibility, will be contacted by the research team to explain the experimental protocol of the trial and to schedule their visits to the Deakin University Burwood Laboratory subsequently. At this point, participants will also be informed to complete a simple three day diet recall, prior to their first visit, using a smartphone app (Easy Diet Diary), to quantify the participants regular dietary intake, establish any dietary allergies and/or sensitivities, as well as, to ensure regular meal timings. This would help identify and eradicate any potential bias to the trial due to irregular meal patterns or extreme calorie restriction which could influence circardian cues and melatonin production (15).

Randomisation

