Participants will be required to report to the university at 17:00 hrs with a fasting period 2.5 hrs before arrival (14:30 hrs). Upon their arrival, simple height and weight measures will be taken by the researchers. Within the first hour of arrival, a trained researcher will insert a cannula into a forearm vein of the participants for blood samples to be taken. Baseline blood and saliva samples will be collected before the experimental supplement consumption. Further, each participant will be provided the experimental ALAC protein shake and a Visual Analog Scale (VAS) -sensory evaluation questionnaire to assess the preference of the ALAC shake at immediately post consumption of the drink (T=0 mins). Participants will also complete a Visual Analog Scale VAS -GI symptoms questionnaire, at two time points i.e. baseline (T=0 mins) and 2hrs post supplement consumption i.e. (T= 120 mins). Small amounts of blood will be drawn (5 mL) at half an hour interval from the time of the supplement consumption (pre supplement and 90 mins, 120 mins, 180 mins and 210 mins post supplement). During the experimental protocol, from T=0 to T= 210 mins, the participants will be asked to relax in an environment consistent lighting and discouraged from using screens. A saliva swab collection will once again be repeated at 3 hrs (210 mins) post supplement consumption. A simple chronotype questionnaire will also be administered to all the participants at this stage. At the end of the study protocol i.e., **21:00hrs**, the participants will be screened for alertness via Karolinska Sleepiness Scale (KSS)(Appendix 4) to assess their ability to drive back home post the intervention and in the event a participant scores >6.8 on the KSS scale, alternate arrangements to travel back home or temporary sleeping arrangements at Deakin University Campus will be made to ensure the participant's safety. Participants will also be handed a boxed dinner meal before leaving the lab. This procedure will be replicated for each of the four visits made be every participant, during the intervention. Participants will also receive a reimbursement via \$100 gift card on successfully completing all 4 intervention sessions.

Wash-out

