8.3 Any participant follow-up

There is no planned follow up following the cessation of the study.

Participants will be provided with a copy of the research report after publication if this option is selected on the consent form

Please ensure your responses to Sections 9-12 comply with Deakin's Research Data Management procedure and accurately reflect the details you have included in your Research Data Management Plan (a compulsory document for all Deakin research).

9. Data Collection/Gathering:

9.1 What information are you going to collect/gather/generate? (as required in addition to that outlined in the HREA)

Please note that prior to the recruitment of the first participant, this clinical trial is to be registered within the ANZCTR.

Personal information

- Name

-Contact number

- Email address (to be sent electronic PLS and consent form, and if selected, publication of study)

Screening measures

- Participant age
- Habitual dietary intake prior to the intervention
- Sleep quality via PSQI questionnaire
- Dietary allergies

-Chronotype measures via morningness eveningness questionnaire (MEQ)

Outcome measures

- Biochemical measures (plasma amino acids and plasma melatonin)
- Palatability of ALAC supplement doses via VAS-GI symptoms questionnaire administered

-Preference of the ALAC supplement doses via VAS -sensory evaluation questionnaire administered

Data Collection

- Blood samples across five timepoints during each intervention session on each of the four separate lab visits i.e., all four supplement doses, to be collected.

-Saliva sample at two time points during each intervention session, on four separate occasions i.e., all four supplement doses to be collected.

9.2 Data collection/gathering techniques: How will you collect/gather the information? Will any third parties be involved in any aspects of recruitment or data collection?

Screening measures

Participant characteristics – age, training level, medication use, alcohol and caffeine consumption, travel history across time zones, recency of night shift work will be collected at baseline using a simple questionnaire (Appendix 1).

Sleep quality – Participants will be screened using the Pittsburgh Sleep Quality Index (Appendix 2) to ensure the participants do not face any pre-existing sleeping difficulties.

Diet Recall - Participants will be asked to record a 3 day diet recall using Easy Diet Diary (EDD) mobile app prior to their first lab visit.

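### Lactose intolerance is flagged for the product in section 14.4 but is not an exclusion in section 7.2, so a lactose-intolerant person is eligible as written

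*Protocol*

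**What the plan says.** Protocol section 14.4, which describes the product, has this entry: "Known contra-indications or warnings Milk protein allergy and lactose intolerance". The same block gives the doses: "Dosage regimen 10g, 20g ,30, 40 g (tryptophan <1.9 g". Under the crossover in section 6.1, each participant takes all four.

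Section 7.2 sets eligibility. Its inclusion criteria cover age and activity level. The only exclusion that concerns milk is in this run: "Excessive beer or wine consumption (>17 standard drinks per week), dairy allergy, high caffeine use".

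Section 9.1 lists, among the screening measures, "Dietary allergies". Section 8.1 asks for a three-day diet recall before the first visit, in part to "establish any dietary allergies and/or sensitivities, as well as, to ensure regular meal timings".

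**The concern.** The Protocol treats milk protein allergy and lactose intolerance as two separate conditions to watch for with this product. It turns only the first into an eligibility rule. The rule that decides who may be dosed therefore admits people whom the product section flags.

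What is at stake is participant safety and a clear instruction to the person who screens. If a volunteer reports lactose intolerance, section 14.4 signals caution, while section 7.2 gives no ground to decline enrolment and no other section says how to handle the case. Eligibility is fixed in the protocol, so this is not a detail that would normally be left to a statistical analysis plan.

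**Working it through.** No arithmetic applies, and the plan states no figure on this point to reproduce. The check sets the relevant sections side by side.

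| Protocol section | Milk protein or dairy allergy | Lactose intolerance |
|---|---|---|
| 14.4, contra-indications or warnings | Named | Named separately |
| 7.2, inclusion criteria | Not mentioned | Not mentioned |
| 7.2, exclusion criteria | Excluded, as dairy allergy | Not mentioned |
| 9.1, screening measures | Covered by dietary allergies | Not mentioned |
| 8.1, three-day diet recall | Covered by allergies | May be picked up as a sensitivity; no exclusion attached |

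1. **Does dairy allergy already cover lactose intolerance?** Section 14.4 lists the two conditions apart. Reading the section 7.2 term to include both would make that separate listing redundant. On the Protocol's own usage, the exclusion matches the first condition and not the second.

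2. **Does any other criterion exclude such a person?** No. The remaining exclusions in section 7.2 concern sleep, sleep aids, alcohol, caffeine, medication, shift work, travel, bedtimes and pregnancy. In the text at hand, lactose is mentioned only in section 14.4.

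3. **Does the diet recall close the gap?** Its wording extends to sensitivities, so an intolerance could be noticed before the first dose. However, section 8.1 asks for it from shortlisted people whose eligibility is already confirmed. Its stated use is to deal with bias from irregular meals or extreme calorie restriction. Nothing says that a reported sensitivity makes a person ineligible.

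4. **Does the screening questionnaire close it?** Appendix 1 is not shown. The summary of its content in section 9.2 mentions neither allergy nor intolerance, but that summary need not be complete. Even if the form asks about lactose, section 7.2 gives no rule by which the answer would exclude anyone.

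5. **Result.** A lactose-intolerant person who meets the other criteria is eligible and, under the crossover, is assigned 10, 20, 30 and 40 g on four separate visits.

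**The case against.** The strongest reply is that section 14.4 uses one combined field for contra-indications and warnings and does not say which applies to lactose intolerance. A contra-indication calls for exclusion, whereas a warning can be met by telling participants. If the entry is only a warning, a section 7.2 list without it is not contradictory. The same block also records no known adverse events. This stands in part: it means that exclusion is not the only acceptable remedy. It does not remove the gap, because the Protocol as shown neither excludes lactose-intolerant people nor says why exclusion is unnecessary.

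A second reply is that the safeguard may sit in the screening questionnaire or the plain language statement. Neither is shown, so it would be wrong to infer that participants are not asked or not warned, and that is not claimed here.

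A third reply is that the diet recall comes before the first dose, and section 9.2 groups it with the screening measures. It does narrow the gap in practice. It does not close it, for want of a rule on what to do with a reported sensitivity.

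A reader might also infer a bias in a secondary outcome. Hypothesis 3 in section 4.3 reads: "The palatability, appetite and preference will reduce at higher ALAC doses". Section 9.1 lists "Palatability of ALAC supplement doses via VAS-GI symptoms questionnaire administered", so intolerance symptoms that rise with dose might seem to favour the hypothesis falsely. The documents do not support that:

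- The lactose content of the product is not given, so the mechanism is conditional on an unknown.
- If the product does contain lactose, gastrointestinal symptoms that rise with dose are an effect of the supplement. That is what the hypothesis sets out to measure, so it is not confounding. At most it affects which population the result describes.
- Section 8.1 schedules the "symptoms questionnaire, at two time points i.e. baseline (T=0 mins) and 2hrs post supplement consumption", and nothing in the Protocol shows that intolerance symptoms would appear within that window.

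**Conclusion.** The inconsistency between sections 14.4 and 7.2 is real and minor. As written, the eligibility criteria admit a person with a condition that the Protocol itself flags for the product, at single doses up to 40 g.

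The conclusion rests on the text alone and on reading dairy allergy as distinct from lactose intolerance, as section 14.4 does. The size of any risk cannot be given: neither the product's lactose content nor the number of people affected can be derived from the Protocol. No harm is shown, and no bias in the primary TRP:LNAA outcome or in palatability is shown. Nor do the documents establish that the entry is a contra-indication; it may be only a warning.

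**What to change.** Add lactose intolerance to the exclusions in section 7.2 beside dairy allergy, and extend the allergy item in section 9.1 to cover it. State that a lactose intolerance reported at screening or in the diet recall meets this exclusion and is acted on before the first dose. The cost is one criterion, one extended screening item and a slightly narrower recruitment pool.

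If the sponsor holds that the product's lactose content is negligible and that the entry is only a warning, say so in section 14.4 instead. That costs a sentence and leaves eligibility unchanged.
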